## Acronyms

2wT	Two-way texting
ART	Antiretroviral Therapy
ARV	Antiretroviral
B2C	Back to Care
DGH	Department of Global Health
DHA	Department of HIV and AIDS
EMRS	Electronic medical records system
HCW	Healthcare worker
HIV	Human Immunodeficiency Virus
HTS	HIV Testing Services
IEC	Information, Education, and Communication
I-TECH	International Training and Education Center for Health
IP	Implementing partner
LH	Lighthouse
LT FU	Loss to follow up
M&E	Monitoring and evaluation
MOH	Ministry of Health
MPC	Martin Preuss Centre
NHSRC	National Health Sciences Research Committee
PI	Principal Investigator
PLHIV	People Living With HIV
RTC	Randomized control trial
SSA	Sub-Saharan Africa
VL	Viral Load
VLS	Viral Load suppression
WHO	World Health Organization
UNAIDS	United Nations
UW	University of Washington

## Executive Summary

In sub-Saharan Africa (SSA), retention of HIV-infection people in antiretroviral therapy (ART) care is an increasing challenge. With only 67% retained on ART in SSA, over 7.5 million people are out of care, threatening both individual health and HIV epidemic control. With significant healthcare system constraints and formidable healthcare worker (HCW) shortages, ART services in SSA struggle to meet ambitious global targets of 90% retained in care. In research settings, text-based mHealth innovations show promise to increase ART retention and, therefore, reduce viral load (VL). However, few mHealth innovations have been tested or proven effective in real-world settings with severe human and financial resource constraints. mHealth innovations that successfully retain more patients on ART within large-volume public ART clinics in SSA are urgently needed. Lighthouse Trust (LT), the largest public provider of ART in Malawi, operates two large clinics in Lilongwe with the Malawi Ministry of Health (MoH), Lighthouse Clinic (LH) and Martin Preuss Center (MPC), with a combined 35,000 ART patients. 12-month retention at Lighthouse is 67%, below the 90% global target for epidemic control. Both clinics employ a real-time electronic medical records system (EMRS) and implement a resource-intensive patient retention program, Back to Care (B2C). B2C aims to trace patients who miss ART visits by  $\geq 14$  days. MPC has over 7800 monthly ART visits, and more than 10% of clients are B2C-eligible. B2C demand, coupled with HCW constraints, results in tracing of only 33% of target clients. Lack of, or delayed, tracing reduces ART retention. Moreover, over 50% of traced B2C clients are found on ART, 60% of whom had transferred, demonstrating significant unnecessary tracing. Poor data quality reduces B2C effectiveness. Therefore, LT and the University of Washington's International Training and Education Center for Health (I-TECH), and Medic Mobile, implemented an innovative, proactive, patient retention system using two-way texting (2wT) between new ART patients and staff. A previous study (#20/06/2565 Two-way Texting (2wT) to Improve Patient Retention While Reducing the Healthcare Workload in High-Burden Public HIV Clinics in Urban Lilongwe) suggested that 2wT improved retention, resolved potential retention issues before they occurred and improved data quality (e.g. identifying transfers), potentially reducing B2C workload. MoH requested a randomized control trial to create more rigorous evidence of 2wT impact. Therefore, with 2wT fully operational, we now implement a pragmatic randomized control at LT trial using routine 2wT teams. The pragmatic RCT will test the existing 2wT intervention to provide adherence support for, and visit-focused communication with, new ART initiates at both LH and MPC clinics, comparing 6-month retention (ART outcomes, visit adherence, VL) and B2C referrals among two groups of new ART clients: 2wT-supported (intervention) and routine B2C (control). With this rigorous evidence, we set the stage for national or regional 2wT scale-up.

## Background

In Malawi, with an estimated 1 million (9%) living with HIV [1], 5-year ART retention falls to 54% [2], stymying progress towards HIV epidemic control [3, 4]. **Reactive retention efforts are resource intensive**, reducing likelihood of scale or sustainably [2]. Lighthouse Trust (LT), a national ART Centre of Excellence in Lilongwe, Malawi, operates with the Malawi Ministry of Health (MoH) to provide HIV care, treatment, and support across Malawi. In its two Lilongwe flagship clinics, 35,000 patients are on ART: 24,000 at Martin Preuse Centre (MPC) and 11,000 at Lighthouse (LH). Patients at both are managed via a real-time, point-of-care, electronic medical records system (EMRS) [5-9]. Despite its prominence, retention at MPC and LH clinics falls short: an average of 67% of ART patients are retained at 12-months, well below the 90% threshold needed for epidemic control [10]. Since 2006, LH and MPC implemented a patient retention program, “Back-To-Care” (B2C), that traces ART patients by phone or home visit who miss a clinic visit by >14 days. B2C has been well-recognized for its success returning patients to care [11-18]. Although early patient tracing increases likelihood of patient reengagement [19], tracing-based retention efforts are reactive -- waiting for clients to miss visits before intervention. B2C and other tracing programs are highly resource intensive [20], limiting scale. At MPC, there are over 7800 scheduled ART visits each month: of these, over 800 clients are presumed LTFU and referred to the 8 full-time B2C tracers. Program resource constraints cause B2C delays and tracing gaps, greatly diminishing B2C effectiveness and retention success. **In December, 2019 only 30% of eligible clients were traced at MPC**, a tracing gap found in other ART programs in SSA [21-23]. Additional proactive retention efforts, within the existing limited resources, are needed to reduce LTFU before it happens.

Myriad mHealth interventions, including text-based, improve ART retention in research settings. However, evidence of successful transfer of these gains to routine ART services delivery in low-resource settings and at scale are missing [24, 25]. With expanding internet access [26], mobile phones are common tools for healthcare needs, even in rural areas [27]. As such, the World Health Organization (WHO) promotes mHealth interventions in low resource settings to support ART adherence [28]. These interventions appear highly acceptable to clients [23, 29-32]. Although mHealth retention efforts aimed at youth [33] or implemented within already-high retention settings (over 80%) may not be effective [34, 35], numerous text-based research interventions significantly increased ART retention (adherence, visit attendance, and viral suppression) among adults [36-45]. Digital innovations also increased engagement among men [23, 38, 46, 47] who are often poor users of health services [48-51]. Interventions that “blast” one-way pre-defined, messages to many people, simultaneously, increase ART adherence [22, 42, 52]. **Interactive, two-way texting (2WT) improves upon blast messaging by encouraging direct client to HCW communication, increasing engagement in care [53] and improving care outcomes [43, 44, 54, 55]**. However, some 2WT intervention require intensive HCW effort, limiting scale-up [44, 56]. mHealth innovations need to provide workload advantages for frontline HCWs who must manage these efforts [54, 57-59].

**We successfully led a 2WT-based randomized control trial (RCT) among male circumcision (MC) clients in a routine MC clinic in Zimbabwe. We improved the quality of care and reduced provider workload by 85% [59] while reducing costs by 33%. Our 2WT extended the reach of HCWs to effectively monitor more patients while improving the quality and**

timeliness of routine data. Both clients and HCWs found the system highly usable and acceptable: 93% of men responded to texts [60]. The routine messages and real-time provider feedback engaged clients as care partners. Similarly, providers received real-time information from clients, allowing for timely reporting of routine data. This project will build on successful 2WT technology developed in Zimbabwe by this team, adapting it for retention efforts in high-burden, public ART programs in Malawi. **Engaging patients in retention efforts could similarly improve client care, data quality and HCW workload at lower cost.**

Lighthouse and its B2C program appear primed for this new kind of task-shifting where mHealth tools enable clients and care givers to exchange information directly and quickly. The hybrid workflow designed for the Zimbabwe RCT integrated the efficiency benefits of automated messaging with the familiarity of SMS on basic phones common in Zimbabwe and Malawi. The intervention also implemented core characteristics of mHealth excellence, including optimizing client accessibility and acceptance; low technology costs, local adaptation, strong stakeholder collaboration, and government partnership for sustained impact [61]. With the same fundamental approach, **our experience suggests ART retention efforts and B2C workload would benefit similarly** because: 1) tracing is burdensome to providers; 2) the intervention enhances routine care quality, minimizing risk; 3) clients can remotely update outcomes in real-time (transfer, travel, other), improving data quality; and 4) frequent visits reduce issues like lost phones, new numbers, etc. [30]. 2wT was successfully tested in 2020-2022 with initial results suggestive of modest increases retention among 2wT participants with high usability and acceptability among LT staff.

The current 2WT improves upon previous texting interventions for retention in several significant ways: 1) Hybrid 2WT with a mix of automated and human-to-human messaging is optimized for staff efficiency by proactively and directly engaging with clients, preventing default (changing visit dates) or ascertaining true outcomes (transfer, stop, etc.); 2) Real-time data provided by clients will improve ART outcome data before 14 days, reducing unnecessary referrals to B2C for tracing and 3) Medic Mobile's open-source intervention software will aid efforts to adapt, maintain, and sustain the system, leveraging the global community of developers to contribute to design improvements in inbox management, message prioritization, or task management.

### *Justification*

Two-way texting, itself, is not novel for retention. However, we developed and evaluated a low-cost 2WT intervention to increase ART retention within a high-volume, routine, public healthcare setting. 2wT is timely, innovative, and programmatically important, aiming to close the gap between what works in research and in routine practice. Lighthouse's hybrid 2wT system among new ART clients at MPC clinic, the largest single clinic for ART patients in Malawi is designed, developed, and initially evaluated with preliminary results appearing positive. The previous study is nearing completion under approved protocol: #20/06/2565 Two-way Texting (2wT) to Improve Patient Retention While Reducing the Healthcare Workload in High-Burden Public HIV Clinics in Urban Lilongwe). This complementary, small-scale, pragmatic randomized control trial (RCT) will strengthen results to inform scale-up while subsequent expansion into routine B2C operations allows for routine evaluation of 2wT in practice. The RCT will provide rigorous evidence for future expansion by implementing 2wT within both LH's and MPC's

existing, public ART program. Comprehensively evaluating 2WT's impact on patient retention and B2C referrals under routine pragmatic conditions will provide real-world evidence of its value, greatly improving the relevance of findings and likelihood of program expansion. Using the RCT results will further optimize 2wT for expansion in routine B2C efforts, supporting LT's retention program. See key innovations: Appendix 6, Table 1.

## Study Objectives:

### *Broad objective:*

To determine if the innovative two-way testing mHealth intervention can significantly increase retention on ART among PLHIV, reducing patient tracing workload.

### *Specific objectives*

1. To determine how much 2-way, visit reminder texting between the Lighthouse clinic and Lighthouse patients can increase new ART client retention and reduce the tracing workload within the first 6 months on ART

## Methods:

### *Overall approach*

**Overview** (See key activities and study timing in Appendix 7, Table 2): Building on the previous 2wT study, this study conducts an RCT for strengthened evidence generation. Over 12 months, we will conduct an RCT in both MPC and LH to prove if 2WT increases 6-month retention (clinic visits, ART outcomes, VL) and reduces workload in both MPC and LH clinics. 6-month outcomes are used as the timeframe is short due to funding constraints. For the RCT, no changes are required in the 2wT software beyond a field for randomization arm. No changes to the educational materials nor to the implementation are needed. The RCT will enroll 410 participants, randomized 1:1 2wT and control. At 6 months, all participants will receive 2wT and continue with 2wT in routine retention activities. The RCT will provide rigorous evidence and generate lessons in direct response to the request of the MoH DHA for more evidence of 2wT impact.

### *Study design*

[figure not shown]
In this current pragmatic RCT study, we randomize eligible 2wT patients who wish to opt-into 2wT, allocating them 1:1 to 2wT and routine Back to Care (B2C) retention efforts. For 6 months, each participant will receive the assigned intervention (2wT or control). At 6 months post enrollment, all RCT participants will receive 2wT and continue with 2wT support as part of routine LT retention activities. We will enroll at both LH and MPC, using results to provide the MoH with data needed to consider 2wT for scale-up.

## Study setting and Population

MPC and LH clinics are in urban Lilongwe, largest public clinic that currently serve over 25,000 patients alive on ART. About 60% of patients are female. On average, MPC and LH clinic initiates **over 800 clients on ART per quarter**, ensuring sufficient pace of enrollment.

## Technology overview

Since 2008, Medic Mobile has been a leader in the global mHealth community [62-68], equipping more than 26,000 health workers serving over 12 million people across 25 countries. Medic Mobile is the steward of the Community Health Toolkit (CHT), an open source project (<https://communityhealthtoolkit.org/>) supporting dozens of mHealth implementations, including 2WT in Zimbabwe. Interventions and apps built using the CHT work with or without internet connectivity, in any language, on basic phones, smartphones, tablets, and computers [69] and are tailored to meet key digital health characteristics recommended by the World Health Organization (WHO) [70]. The core areas of functionality used by the current 2WT system include peer-to-peer and automated interactive messaging, task management features (unread message; message not delivered), longitudinal patient records, data collection forms, routine syncing, and dashboard reports for routine monitoring (e.g. client response rates, referrals, etc.) [58]. Together, these features will enable an integrated 2WT workflow tailored to ART retention, generating the data needed to monitor program delivery and facilitate research. The CHT also supports interoperability with other eHealth tools (via the NIH-supported FHIR standard [71] or custom data formats). The existing 2WT flow diagram is illustrated below.

## *Staff training*

All staff at LH and MPC will be informed of the study and briefed on study protocols. A 2WT study coordinator, selected from current staff, will be trained in confidentiality, protection of human subjects, enrollment, randomization, and data collection methods. This person will manage enrollments, randomization, and the 2WT database, including text and voice follow-up communication with intervention clients. Malawi-based co-investigators, including MoH collaborators, will also be invited for Medic Mobile training.

## *Sample size calculation*

Supposing a two-arm prospective study with 3-4 months recruitment period and 6 months follow-up. Assume the hazard for the control group is a constant risk over time at 0.2 (20%). To achieve 80% power to detect a hazard ratio of 0.41 in the exposed group by using a two-sided 0.05-level log-rank test, the required sample size per arm is 197. With an estimated dropout of 10%, 410 (205 per arm) will be needed, and up to 500 will be enrolled, total, to allow for buffer and withdrawal of those with lack of SMS confirmation receipt (documented).).

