## *Study outcomes*

Primary retention outcomes: 1) Proportion of patients retained in care at 6-months; (2) visit attendance; and 3) VL (suppressed = HIV RNA < 400 copies). Primary workload outcome is cumulative B2C referrals at 6 months. Secondary outcomes include: Text response rates, #visit date change requests, #ART outcomes updated, % of failed messages, client contact number updates, % referral of true LTFU for tracing, and B2C tracing outcomes (transfer, stop, alive, etc.).

Table: Outcomes	Definition	Source	Phase	
Individual level (Reach and Effectiveness):			R21	R33
Retention outcomes				
Retention	6-month ART retention (alive on ART or client report of transferred care)	EMRS	X	X
ART visit adherence	% of visits attended		X	X
Viral load	% suppressed (HIV RNA <400 copies)			
Workload outcome:				
Healthcare workload	# cumulative B2C referrals at 6 months; time spent on 2WT and B2C	Time-motion, EMRS, 2WT database	X	X

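### The 197 per arm for 80% power does not match the trial's 6-month comparison: the control hazard has no time unit, and no plausible unit gives 197 with 6 months at risk each

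*Combined protocol and SAP*

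**What the plan says.** Under Sample size calculation the protocol sets the timing: "Supposing a two-arm prospective study with 3-4 months recruitment period and 6 months follow-up". The control rate follows: "Assume the hazard for the control group is a constant risk over time at 0.2 (20" (the quote stops just before the per cent sign and closing bracket). No time unit is attached. For a hazard ratio of 0.41, 80% power and a two-sided 0.05 log-rank test, "the required sample size per arm is 197". The dropout step is "With an estimated dropout of 10%, 410 (205 per arm) will be needed". The same sentence then sets an enrolment ceiling above that figure: "up to 500 will be enrolled, total, to allow for buffer and withdrawal of those with lack of SMS confirmation receipt".

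Other sections bear on this:

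- Study design puts each participant on the assigned arm for 6 months, after which everyone receives two-way texting. The last sentence of the Retention analysis section has the RCT arms compared at 6 months.
- The Executive Summary states "12-month retention at Lighthouse is 67%, below the 90% global target for epidemic control", and Background repeats "an average of 67% of ART patients are retained at 12-months".
- Limitations and uncertainties gives a study retention target of 82%, described as a 15% increase.
- Study outcomes defines retention as "6-month ART retention (alive on ART or client report of transferred care". Routine ART initiation procedures lists loss to follow-up among the recorded ART outcomes.
- Overall approach and Randomization give 410 only.

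**The concern.** A hazard is a rate. Without its time unit it cannot be turned into expected events, and a log-rank calculation depends on events. The section also leaves out the event count, the formula and the follow-up model, so a reader cannot tell how 197 was reached or whether it applies to a 6-month comparison. The dropout step adds a second doubt: the usual inflation of 197 for 10% loss does not give 205.

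What is at stake is the 80% claim. If the unit is annual, the trial has clearly less power than stated for a hazard ratio of 0.41; if it is 6-monthly, it has more. The Ministry of Health asked for this trial as stronger evidence, so readers will want to know what size of effect it could detect.

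**Working it through.** **Inputs.** From Sample size calculation: hazard ratio 0.41, two-sided alpha 0.05, power 80%, control hazard 0.2 (20%), dropout 10%, and 197 and 205 per arm. From Study design and the Retention analysis section: 6 months at risk each. Assumption: exponential survival, as the constant hazard implies. The unit of the hazard is also an assumption, so the range is shown.

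**Events (Schoenfeld).** 4 × (1.960 + 0.842)² / (ln 0.41)² = 4 × 7.849 / 0.795 = 39.5.

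**Trying to reproduce 197.** With hazard h per month, pC = 1 − exp(−6h) and pT = 1 − exp(−6 × 0.41h). Then n per arm = 39.5 / (pC + pT). Power at 205 per arm = Φ(√(d/4) × |ln 0.41| − 1.960), with d = 205 × (pC + pT).

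| Reading of the hazard | pC | pT | n per arm | d at 205 | Power at 205 |
|---|---|---|---|---|---|
| 0.2 per year | 0.0952 | 0.0402 | 291.8 | 27.7 | 65% |
| 20% by 12 months | 0.1056 | 0.0447 | 262.8 | 30.8 | 70% |
| 0.2 per 6 months | 0.1813 | 0.0787 | 151.9 | 53.3 | 90% |
| 20% by 6 months | 0.2000 | 0.0874 | 137.4 | 58.9 | 93% |
| 0.2 per month | 0.6988 | 0.3886 | 36.3 | 222.9 | near 100% |

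None is 197. Freedman's formula gives 333, 300, 174, 157 and 42 in the same order; a two-proportion formula gives 327, 294, 168, 152 and 40. Simulated log-rank power at 197 per arm is 61%, 66%, 87% and 91% for the first four readings.

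**Where numbers near 197 do arise.** Averaging the event probability over uniform entry:

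- 20% by 12 months, 4 months' accrual plus 6 months' follow-up (6 to 10 months each): pC = 0.1380, pT = 0.0591, n = 200.3. With 3 months' accrual, n = 212.8.
- 0.2 per 6 months, 3 months' recruitment inside a 6-month total (3 to 6 months each): pC = 0.1389, pT = 0.0596, n = 198.9.
- 20% by 6 months, recruitment of 3 to 4 months inside a 6-month total: n = 179.6 to 201.0.

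The first counts time after controls have moved to texting. The other two give most participants less than 6 months.

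**The protocol's own retention figures.** Take 67% and 82% as 12-month retention under constant hazards (an assumption, since the 82% carries no time point). The hazard ratio is ln 0.82 / ln 0.67 = 0.1985 / 0.4005 = 0.496. At 6 months, pC = 1 − √0.67 = 0.1815 and pT = 1 − √0.82 = 0.0945. At 205 per arm d = 56.6, and power = Φ(√(56.6/4) × 0.702 − 1.960) = 75%. At 184.5 per arm d = 50.9 and power is 71%.

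**Dropout, taking 197 as given.**

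- Removal from analysis: 197 / 0.9 = 218.9, so 219 per arm or 438 in total. 205 absorbs 1 − 197/205 = 3.9%. After 10% removal 205 × 0.9 = 184.5 remain, and power is Φ(2.802 × √(184.5/197) − 1.960) = 77%.
- Exponential censoring with 6 months at risk: 10% by 6 months multiplies n by about 1.052, giving 207 (206 on the monthly reading). 10% by 12 months multiplies it by about 1.026, giving 202 (201 on the monthly reading).
- Enrolment of 500 is 250 per arm. After 10% removal 225 remain, and power is Φ(2.802 × √(225/197) − 1.960) = 85%.

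**The case against.** The strongest reply is that 6 months at risk each is not in the sample size section. That section gives a recruitment period as well as follow-up, and recruitment length matters in a log-rank calculation only with staggered entry and a common close. Read that way, with 4 months' recruitment and 20% by 12 months, it yields 200.3, within 2% of 197. This stands: a reader might infer that the figure fails on its own section's inputs, and that would go too far. What remains is that such a calculation does not describe the comparison the trial will make.

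A reader might also infer that the trial is underpowered. The documents do not support that, because the 6-monthly and monthly readings give 90% power or more for 0.41.

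The opposite inference is equally tempting. Retention of 67% at 12 months is a hazard of −ln 0.67 = 0.40 per year, or 0.20 per 6 months, so 410 looks ample at 90%. But the protocol does not make that link, that reading gives 152 rather than 197, and pairing the same 67% with the 82% target gives a hazard ratio near 0.50.

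An unpooled two-proportion formula for 20% against 10% gives exactly 197. However, 10% is not a stated input and implies a hazard ratio of 0.47, so this may be coincidence.

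On dropout, calling 205 an arithmetic error would be too strong. Under censoring about 205 is reasonable. The ceiling of 500 could also cover 438, leaving 62, if withdrawals for a missing confirmation text do not use it up.

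Finally, retention will be compared by chi-square with a relative risk and 95% interval, so a null result can be read from the interval and does not rest on planned power alone.

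**Conclusion.** The concern holds in this form: 197 per arm for 80% power at a hazard ratio of 0.41 is not reproduced for 6 months at risk per participant under any of five readings of the unlabelled hazard (292, 263, 152, 137 or 36 per arm). The missing unit alone moves power at 205 per arm from 65% to nearly 100%. Neither a shortfall nor adequacy is established. The protocol's own 67% to 82% gives about 75% at 205 per arm, or 71% after 10% removal, if both are 12-month figures under constant hazards.

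The dropout step is secondary and conditional. It falls short (219 needed, about 77% power) only if dropout means removal, 197 is right and enrolment stops at 410. Loss to follow-up already counts as non-retention and reported transfers count as retained, so it is unclear who would be removed.

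This should be fixed, mainly because of the missing unit and follow-up convention.

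**What to change.** In Sample size calculation:

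- State the time unit of the control hazard and its source, the number of events, the formula, and the follow-up per participant.
- Recompute for 6 months at risk each.
- Reconcile the hazard ratio of 0.41 with the 67% to 82% target in Limitations and uncertainties, giving the time point of that target.
- Say whether dropout is removal or censoring, over what period, and who would leave the retention analysis.
- Restate the power that 410 delivers.
- Add one sentence saying that 410 is the net randomised target and 500 the gross ceiling, if that is what is meant, and use it consistently in Overall approach and Randomization.

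The cost is text only, with no added enrolment. The downside is that the stated power may become less favourable.
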